## **6.4 EFFICACY ANALYSES**

The primary and secondary efficacy analyses will include all randomized patients who received any study medication, with patients grouped according to the treatment assigned at randomization.

### **6.4.1 Primary Efficacy Endpoint**

The primary assessment of efficacy of obinutuzumab, to induce a clinically significant improvement in renal function in patients with ISN/RPS 2003 class III or IV LN, will be assessed by attainment of CRR.

CRR is defined as achievement of all of the following:

- Normalization of serum creatinine as evidenced by the following:
  - Serum creatinine  $\leq$  the ULN range of central laboratory values if the baseline (Day 1) serum creatinine is above the ULN
  - Serum creatinine  $\leq$  15% above baseline and  $\leq$  the ULN range of central laboratory values if baseline (Day 1) serum creatinine is  $\leq$  the ULN range of central laboratory values
- Inactive urinary sediment (as evidenced by  $< 10$  RBCs/HPF and the absence of red cell casts)
- Urinary protein to creatinine ratio  $< 0.5$

Any patient who switches to rescue medication prior to Week 52 will be considered a non-responder. Additional criteria for analyses of patients who are considered non-responders will be specified in the SAP.

The proportions of patients achieving CRR across treatment groups will be compared using a CMH test with race (Afro-Caribbean/African American versus others) and region (United States versus non-United States) as stratification factors. If the test result is in favor of the obinutuzumab group at  $\alpha < 0.1$ -level (one-sided), it will be concluded that there is a shift toward better renal response associated with the obinutuzumab group.

#### **6.4.2 Secondary Efficacy Endpoints**

The proportion of patients who achieve an overall response at Week 52 (CRR+PRR) will be analyzed using a CMH test, with race and region as strata.

The proportion of patients achieving PRR at Week 52 as defined by achievement of all of the following:

- Serum creatinine  $\leq 15\%$  above baseline value
- No urinary red cell casts and either RBCs/HPF  $\leq 50\%$  above baseline or  $< 10$  RBCs/HPF
- 50% improvement in the urine protein to creatinine ratio, with one of the following conditions met:
  - If the baseline urine protein to creatinine ratio is  $\leq 3.0$ , then a urine protein to creatinine ratio of  $< 1.0$
  - If the baseline protein to creatinine ratio is  $> 3.0$ , then a urine protein to creatinine ratio of  $< 3.0$

Time to first overall response (CRR+PRR) over the course of 52 weeks will be presented using Kaplan-Meier methodology and compared between treatment groups using a stratified log-rank test with race and region as strata. Time to CRR during this period will be analyzed similarly.

The percent change from baseline and mean and median assessments of biomarkers of LN disease activity will be analyzed using appropriate statistical methodology.

The proportions of patients who achieve a CRR at Week 24 will be analyzed using the same methodology as the primary analysis. In addition, the modified definitions, mCRR1, mCRR2, and mCRR3, of CRR will be analyzed in this way to assess the sensitivity of CRR to its definition.

Sensitivity analyses will be performed to assess the potential impact on the primary endpoint, and possibly also key secondary endpoints, of missing data and possibly also changes to background immunosuppressive medication.

The secondary, sensitivity, PRO, and exploratory analyses will be fully specified in the SAP.

#### **6.4.3 Exploratory Efficacy Endpoints**

The exploratory outcome endpoints for this study are:

- Change in B-cell subsets over the course of the study
- Change in serum and urine biomarkers over the course of the study
- Proportion of patients experiencing an extrarenal flare over 52 weeks
- Proportion of patients experiencing a renal flare over 52 weeks and 104 weeks
- Proportion of patients achieving CRR, mCRR1, mCRR2, and mCRR3, at additional timepoints, including Week 12 and Week 36
- Change in Physician's Global Assessment over 52 weeks
- Change in GTCl over 52 weeks
- Change in Renal biopsy histopathology over time

### **6.5 SAFETY ANALYSES**

The safety analyses will include all randomized patients who received any study drug, with patients grouped according to the treatment actually received.

#### **6.5.1 Adverse Events**

Adverse events will be coded according to a standardized thesaurus. The severity of adverse events will be classified using the NCI CTCAE, Version 4.0.

The number and percentage of patients who experience an adverse event will be summarized by mapped term, appropriate thesaurus level, and toxicity grade for each treatment group. Separate summaries will be provided for serious adverse events, treatment-related adverse events (defined as any adverse event occurring during or within 24 hours following the completion of a study drug infusion), infusion-related adverse events and adverse events leading to study discontinuation.

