### **5.1.2 Infections**

Serious bacterial, fungal, and new or reactivated viral infections can occur during and following the completion of obinutuzumab therapy. Fatal infections have been reported.

Obinutuzumab is more potent in B-cell depletion than is rituximab; it is theoretically possible that there is an increased risk of infections with obinutuzumab compared with rituximab. Study BO21004/CLL11 provides the most meaningful assessment of the possible risk of infection (Goede et al. 2014). In Stage 1a (obinutuzumab+chlorambucil versus chlorambucil alone) and Stage 2 (obinutuzumab+chlorambucil versus rituximab+chlorambucil) of Study BO21004 in patients with CLL, the incidence of infections was similar between the treatment arms. However, the chlorambucil arm compared with the obinutuzumab+chlorambucil arm showed a higher incidence of serious infections and deaths due to infection; the incidence of serious infections and fatal infections was similar in the obinutuzumab+chlorambucil and rituximab+chlorambucil arms. To date, there is no clear evidence of a difference between rituximab and obinutuzumab regarding infections.

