### **5.3.4 Assessment of Causality of Adverse Events**

Investigators should use their knowledge of the patient, the circumstances surrounding the event, and an evaluation of any potential alternative causes to determine whether or not an adverse event is considered to be related to the study drug, indicating "yes" or "no" accordingly. The following guidance should be taken into consideration (see also Table 8):

- Temporal relationship of event onset to the initiation of study drug
- Course of the event, considering especially the effects of dose reduction, discontinuation of study drug, or reintroduction of study drug (as applicable)
- Known association of the event with the study drug or with similar treatments
- Known association of the event with the disease under study
- Presence of risk factors in the patient or use of concomitant medications known to increase the occurrence of the event
- Presence of non-treatment-related factors that are known to be associated with the occurrence of the event

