**Table 8 Causal Attribution Guidance**

Is the adverse event suspected to be caused by the study drug on the basis of facts, evidence, science-based rationales, and clinical judgment?	
YES	There is a plausible temporal relationship between the onset of the adverse event and administration of the study drug, and the adverse event cannot be readily explained by the patient's clinical state, intercurrent illness, or concomitant therapies; and/or the adverse event follows a known pattern of response to the study drug; and/or the adverse event abates or resolves upon discontinuation of the study drug or dose reduction and, if applicable, reappears upon re-challenge.
NO	An adverse event will be considered related, unless it fulfills the criteria specified below. Evidence exists that the adverse event has an etiology other than the study drug (e.g., preexisting medical condition, underlying disease, intercurrent illness, or concomitant medication); and/or the adverse event has no plausible temporal relationship to administration of the study drug (e.g., cancer diagnosed 2 days after first dose of study drug).

For patients receiving combination therapy, causality will be assessed individually for each protocol-mandated therapy.

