#### **5.3.5.1 Infusion-Related Reactions**

Adverse events that occur during or within 24 hours after study drug administration and are judged to be related to obinutuzumab infusion should be captured as a diagnosis (e.g., "infusion-related reaction") on the Adverse Event eCRF. If possible, avoid ambiguous terms such as "systemic reaction." Associated signs and symptoms should be recorded on the dedicated Infusion-Related Reaction eCRF. If a patient experiences both a local and systemic reaction to the same dose of study drug, each reaction should be recorded separately on the Adverse Event eCRF, with signs and symptoms also recorded separately on the dedicated Infusion-Related Reaction eCRF.

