4.8.2 Adverse Events

Adverse events will be mapped and reported using the Medical Dictionary for Regulatory Activities (MedDRA) thesaurus using the most current version at the time of analysis (Version 20.1 or later). Glossaries showing the mapping of investigator verbatim terms to coded events will be produced.

Treatment-emergent adverse events (TEAEs) will be summarized. All AEs referenced in the section below will be TEAEs. TEAEs are defined as those AEs with observed or imputed onset date on or after the start date of trial treatment. Only where the most extreme intensity is greater than the initial intensity (or if most extreme intensity is not missing and initial intensity is missing) will events with an onset date prior to the start of trial treatment be considered treatment-emergent. An AE with a completely missing start date will be assumed to be treatment-emergent unless the AE has a complete non-imputed end date that is prior to study Day 1.

Listings will show all AEs reported, including AEs occurring after rescue therapy, and any AEs that may have occurred during the oral corticosteroid dose adjustments in the screening period.

AEs will be summarized by system organ class (SOC) and preferred term (PT), and will be presented in order of descending frequency summed across the treatment arms within each SOC and PT.

The following will be summarized, and/or listings produced where required:

- All AEs
- Serious Adverse Events (SAEs)
- AEs by relationship to obinutuzumab/placebo
- AEs by relationship to MMF/MPA
- Corticosteroid-related adverse events
- AEs leading to study drug dose modification or interruption
- AEs by common terminology criteria grade
- Infections
- Serious Infections
- Infusion related reactions (IRRs)
- Serious IRRs

Obinutuzumab—F. Hoffmann-La Roche Ltd

Statistical Analysis Plan

WA29748

- AEs leading to withdrawal
- AEs leading to death

AEs to monitor will be listed, including:

- Opportunistic infections (Roche Standard AE Grouped Term [AEGT] Basket)

AE rates per 100 patient-years exposure will be produced for key safety events. Rates will be based on all occurrences of AE. AE rate per 100 patient-years is defined as:

$$(\text{number of events} \div \text{total exposure}) \times 100$$

The 95% confidence intervals (CIs) will be calculated based on exact poisson distribution.

Positive pregnancy results will be listed, as identified using the serum test results.

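### Protocol 6.5.1 defines treatment-related adverse events by a 24-hour clock with no causality judgement, contradicting the protocol's own causality rule and differing from SAP 4.8.2

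*Protocol*

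**What the plan says.** Protocol 6.5.1 (Adverse Events) lists several separate summaries. One is for "treatment-related adverse events (defined as any adverse event occurring during or within 24 hours following the completion of a study drug infusion". The next items in the same sentence are "infusion-related adverse events and adverse events leading to study discontinuation", and the infusion-related category is given no definition there.

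Three other places bear on the same terms:

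- **Protocol 5.3.4 and Table 8.** Investigators use their knowledge of the patient and the circumstances "to determine whether or not an adverse event is considered to be related to the study drug", answering yes or no. Table 8 sets the default: "An adverse event will be considered related, unless it fulfills the criteria specified below". Under combination therapy, causality is assessed separately for each protocol-mandated therapy. Section 5.3 requires a causality assessment for every adverse event on the eCRF.
- **Protocol 5.3.5.1.** The recording rule for infusion-related reactions covers "Adverse events that occur during or within 24 hours after study drug administration and are judged to be related to obinutuzumab infusion". It needs both the timing and the judgement.
- **SAP 4.8.2.** The planned outputs include "AEs by relationship to obinutuzumab/placebo", a matching item for MMF/MPA, and "Infusion related reactions (IRRs") as an item of its own. No 24-hour rule appears, and the SAP does not mention the 6.5.1 definition.

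**The concern.** Relatedness and timing are different attributes of an event. Section 6.5.1 gives a table the name of the first and fills it by the second. Followed as written, the table misclassifies in both directions. An event that the investigator judged related is left out if it starts more than 24 hours after an infusion ends. An event judged unrelated is included if it starts on an infusion day.

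The omitted side matters because the protocol expects delayed effects. Section 5.1.2 says: "Serious bacterial, fungal, and new or reactivated viral infections can occur during and following the completion of obinutuzumab therapy". Table 6 notes late-onset neutropenia 28 days after the end of treatment, reported in studies of hematologic malignancy. Characterizing infections and neutropenia is a stated safety objective (Section 2.2), and drug-related neutropenia and thrombocytopenia are adverse events of special interest (Section 5.2.3).

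Two analysts, one working from the protocol and one from the SAP, would produce different related-event tables from the same data, and neither document says which takes precedence.

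**Working it through.** No sample size, power or alpha figure depends on this definition, so there is no stated number to reproduce. The check is a comparison of the texts, followed by a measurement of the window.

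**1. The definitions side by side**

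| Place | Term | Time limit | Relatedness judged? |
|---|---|---|---|
| Protocol 6.5.1 | Treatment-related | During infusion or up to 24 h after it ends | No |
| Protocol 6.5.1 | Infusion-related | None given | Not stated |
| Protocol 5.3.4, Table 8 | Related to study drug | None | Yes |
| Protocol 5.3.5.1 | Infusion-related reaction | During or up to 24 h after administration | Yes |
| SAP 4.8.2 | By relationship to obinutuzumab/placebo | None | By relationship; assessor not named |

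The first row agrees with neither the third nor the fifth. Its timing is that of the fourth row, without the relatedness condition. A definition attached to the wrong term would explain this, since the infusion-related category that follows it has none. That explanation is an inference.

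**2. How single events would be classified**

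- Onset on Day 40, judged related: related under 5.3.4 and Table 8, but not treatment-related under 6.5.1.
- Onset during the Day 15 infusion, judged unrelated: not related under 5.3.4, but treatment-related under 6.5.1.
- Neutropenia starting 28 days after the last infusion, on Day 182 + 28 = Day 210: outside every window whatever the investigator's judgement, because the last window closes on about Day 183.

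**3. Length of the windows**

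Inputs: four infusions, on Days 1, 15, 168 and 182 (Protocol 4.3.2.1); planned durations of 255 min for the first and 195 min for each later one (Appendix 7, Tables 1 and 2); follow-up to Day 364 (Week 52) and Day 728 (Week 104).

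- Infusion time: 255/60 + 3 × 195/60 = 4.25 + 9.75 = 14 h
- Post-infusion time: 4 × 24 = 96 h
- Total: 14 + 96 = 110 h; 110/24 = 4.58 days
- Share of time to Week 52: 4.58/364 = 1.26%
- Share of time to Week 104: 4.58/728 = 0.63%

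Leaving out the infusions themselves gives 96/24 = 4.0 days, or 1.10% and 0.55%. Slowed or interrupted infusions would lengthen the windows by hours and not alter the picture. Under Section 5.3.1 all adverse events are reported to Week 104 or for 76 weeks after the last dose, whichever is longer. For a patient dosed on schedule the second limit is Day 182 + 532 = Day 714, so 728 days is the relevant period.

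**The case against.** The strongest answer is that the consequence is small, and much of that stands.

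First, the SAP governs the final CSR, and 4.8.2 already tabulates by relationship with no 24-hour rule. Nothing in the documents shows that a table built to 6.5.1 is planned for that report. This limits the practical effect. It does not remove the contradiction, because the SAP neither says whose assessment relationship means nor declares that it departs from 6.5.1. Reading it as the investigator's recorded judgement is reasonable given 5.3.4, but it is an inference. The Week 52 and Week 104 CSRs have already been issued, and the documents do not show which definition they used.

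Second, a reader might infer that the definition hides delayed harms or makes obinutuzumab look safer overall. The documents do not support that. Section 6.5.1 also summarizes all adverse events by term and grade, and serious events, with no time limit. Section 6.5.3 covers treatment-emergent laboratory abnormalities and neutrophils. SAP 4.8.2 adds infections, serious infections, a listing of opportunistic infections, and rates per 100 patient-years for key events. Protocol 5.4 requires serious events and events of special interest to be reported regardless of relationship. The comparison between arms on these outputs is untouched.

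Third, a reader might take 0.63% to mean that more than 99% of related events would be missed. It does not mean that. Infusion reactions were the most frequent adverse drug reactions in earlier obinutuzumab studies (Section 5.1.1), and they cluster inside the windows. The share of related events outside them cannot be calculated from the documents.

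Fourth, 5.3.4 instructs sites while 6.5.1 labels a table, so no site action is contradictory and recorded causality is unaffected. That is correct. The conflict is between the recorded judgement and the table that carries its name.

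**Conclusion.** The point holds as a definitional error confined to one safety summary. Section 6.5.1 is wrong as written: it calls events treatment-related on timing alone, against the protocol's causality rule, and differs from the SAP. It would change the content of the protocol-defined related-event table in both directions, and late events judged related could not enter it. Those events would be mislabelled there and would remain visible in the all-event, serious-event, infection and laboratory summaries.

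The windows amount to about 4.6 of 728 days, assuming all four infusions run to the planned times. This shows how narrow the definition is in calendar time; the number of events affected is unknown. Infections and late-onset neutropenia carry the argument, because the documents describe their late timing. They give no onset time for progressive multifocal leukoencephalopathy, so the point does not rest on it.

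If the final CSR follows SAP 4.8.2, the effect on that report is small. No efficacy result, sample size or error rate is touched.

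**What to change.** In Protocol 6.5.1, define treatment-related adverse events as those with a recorded causality assessment of yes under 5.3.4 and Table 8. Attach the 24-hour window to infusion-related adverse events, together with the relatedness condition of 5.3.5.1.

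If the protocol is not to be amended again, add one sentence to SAP 4.8.2 saying that relationship means the investigator's recorded assessment and that this replaces the 6.5.1 definition. In the final CSR, state which definition was used.

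The cost is one sentence of protocol or SAP text. The protocol route also needs an amendment submission to IRBs/ECs and regulatory authorities under Section 9.6, so the SAP route is cheaper at this stage. No new data are needed, because causality is already assessed for every recorded adverse event.

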#### **6.5.2 Deaths**

Patient deaths, including the primary cause of death, will be summarized.

#### **6.5.3 Laboratory Tests**

Descriptive statistics of laboratory values and the change from baseline (Day 1) will be presented for each treatment group. The number and percentage of patients with treatment-emergent laboratory abnormalities will be presented for each treatment group. Laboratory measurements will include serum chemistries; urinalysis; hematology; plasma immunoglobulins; and circulating B-cells, T-cells, neutrophils, and other cell populations.

The number and percentage of patients with positive serum antibodies to obinutuzumab at baseline and during the treatment period will be tabulated.

#### **6.5.4 Vital Signs**

The change from pretreatment (measured just before initiation of the infusion) in vital signs recorded during infusion and post-infusion will be summarized. Vital signs that are obtained during screening and the follow-up period will also be summarized.

### **6.6 PHARMACODYNAMIC ANALYSES**

The primary PD marker will be CD19+ B-cell counts. Exploratory PD markers from blood samples will be summarized graphically and descriptively over time by cohort; these markers include B-cell subsets, and quantitative Ig levels (total, IgG, IgM, and IgA). In addition, the percent change from baseline for each marker will be computed at each sampling timepoint using the Day 1 pre-dose value as the baseline point.

Potential PD markers specific to SLE/LN will be summarized graphically and descriptively as appropriate and may include but are not limited to the following:

- Markers of inflammation or B-cell activation: BAFF, proteinuria, and C3 and C4 complement
- Autoantibodies: ANA, anti-dsDNA, Sm, Ro, La, RNP, and others

Exploratory analyses will be performed to assess the possible relationship between obinutuzumab dosing, PD markers, PK measures, and clinical response. The key exploratory analyses will be specified in the SAP.

### **6.7 PHARMACOKINETIC ANALYSES**

PK parameters derived from serum concentrations of obinutuzumab will be computed by the following:

- Maximum serum concentration
  - During the entire study ( $C_{max}$ )
  - After the first course of study drug ( $C_{max1}$ )
  - After the second course of study drug ( $C_{max2}$ )
- AUC from
  - Time 0 to infinity ( $AUC_{0-\infty}$ ) based on all four infusions
  - Time 0 to 336 days ( $AUC_{0-336}$ ) based on all four infusions
  - Time 0 to 168 days ( $AUC_{0-168}$ ) based on the first two infusions
  - Time 168 to 336 days ( $AUC_{168-336}$ ) based on the third and fourth infusions
- Systemic clearance
- Volume of distribution under steady-state conditions ( $V_{ss}$ )

- Half-life ( $t_{1/2}$ ) for the terminal portion of the serum concentration–time curve after both courses of treatment

PK parameters will be determined for all patients with serum concentration data by the method that best describes the data. This may be non-compartmental analysis, compartmental analysis for each individual patient, or population PK analysis. PK parameters will be computed for all patients with serum concentration data except for patients who are noncompliant to dosing and/or sampling schedule or whose samples have interference by ADAs (which precludes data inclusion); these patients will be excluded from the analysis.

PK analysis will include an exploratory analysis to identify baseline covariates that affect the pharmacokinetics of obinutuzumab in this patient population. Baseline covariates that will be examined include demographics, other patient characteristics (such as disease severity), and selected laboratory measures.

No hypothesis testing will be performed using the PK parameters. PK data will be summarized using descriptive statistics, including mean, standard deviation, geometric mean, coefficient of variation, median, and range.

Additional PK analyses will be conducted as appropriate.

